4.2.11.5 Sensitivity Analyses of the Tertiary/Exploratory Endpoint

Not applicable

4.2.11.6 Supplementary Analyses of the Tertiary/ Exploratory Endpoint

Not applicable

4.2.11.7 Subgroup Analyses

Not Applicable

4.3 Pharmacodynamic Endpoint(s)

4.3.1.1 Definitions and Derivations

Sputum samples will be collected for pharmacodynamic assessments at SV3(Baseline) and SV5(Week 12).

The target engagement will be defined as:

$$100 \times \frac{MPO\ Activity}{MPO\ Concentration}$$

Change from baseline in target engagement to Weeks 12 will be calculated as specified in Section 3.3.1.2.

4.3.1.2 Presentation

The normalised MPO activity and its change from baseline will be summarised using descriptive statistics.

Change from baseline to Weeks 12 in normalised MPO activity will be analysed using a ANCOVA as described in Section 3.4.2.

LSMean change from baseline and two-sided 90% CI to Weeks 12 in normalised MPO activity will be presented.

Participants who had intercurrent events will be included for analysis using treatment policy strategy.

Treatment policy strategy means if an intercurrent event occurs all subsequent data for that participant up to last dose are included in the evaluation.

4.4 Pharmacokinetics

4.4.1 Definitions and Derivations

Blood samples will be collected for measurement of plasma concentrations of AZD4831 at the following timepoints:

- Day 1 Pre-dose
- Week 12:
 - o Pre-dose
 - Post-dose (for approximately 20% of participants)
 0.5h to 1.5h post-dose and 1.5h to 3h post, with a minimum of 1h between the post-dose sampling occasions.

Plasma samples will be used to analyse the PK of AZD4831. Samples collected for analyses of AZD4831 concentration may also be used to evaluate safety or efficacy aspects related to concerns arising during or after the study.

Pharmacokinetic data for those participants with additional PK sampling at Week 12 will be used to derive plasma PK parameters.

Cmax	Maximum observed plasma concentration
Tmax	Time to reach peak or maximum observed concentration following drug administration
Ctrough	Observed lowest concentration before the next dose is administered

Additional PK parameters may be determined where appropriate.

The derivation of PK parameters from the plasma concentration for AZD4831 will be performed by AstraZeneca CPK scientist team, in accordance with AZ Global Guidance for Non-Compartmental Pharmacokinetic Evaluations in Clinical Studies.

Pharmacokinetic analysis will, where possible, be carried out using actual times determined from the PK sampling and dosing times recorded in the raw data.

4.4.2 Presentation

The PK concentrations and PK parameters will be listed and presented in tabular and graphical form, as appropriate, according to the version of the AstraZeneca Corporate templates and reporting standards as documented in the TFL shells, that include applicable descriptive statistics, defined handling of individual concentrations BLQ and precision/rounding rules for PK concentration and parameter data.

Plasma AZD4831 concentrations will be summarised using descriptive statistics (including geometric mean, CV%) for all timepoints at each visit by study intervention group on PK set and will be listed for each patient from the SS.

Geometric mean (together with gSD) serum AZD4831 concentration over time will be plotted on both linear and semi-logarithmic scales for Week 12 based on PK set. For the 0.5h to 1.5h sample and 1.5h to 3h sample, the geometric mean will be plotted at the midpoint of the collection window (ie 1h and 2.25h respectively).

Individual and combined individual serum AZD4831 concentration vs actual time plots will be provided for the 20% of participants with post-dose PK sampling at Week 12 on both the linear and semi-logarithmic scale.

4.5 Immunogenicity

Not applicable

4.6 Genetics

Not applicable.

4.7 Safety Analyses

The domain safety covers exposure, adverse events, clinical laboratory, vital signs, ECG and physical examination.

Tables are provided for the safety set; listings are provided for All participants or the safety set depending on the availability of data.

The safety analysis will not be performed as planned in the CSP using estimand strategy. The analyses of adverse events will include all data reported, which includes all data up to the end of the study period including the treatment and follow-up periods, starting from date of the first dose of IP and ending on the earliest date of withdrawal of consent or date of death or last study visit (SV8). For other safety analysis (ie, labs, vital signs), all data up to the end of the study period including the treatment and follow-up periods starting from baseline or screening data and ending on the earliest date of withdrawal of consent or date of death or last study visit (SV8).

4.7.1 Exposure

4.7.1.1 Definitions and Derivations

Exposure duration is calculated only for participants in the Safety population as the total number of days on study drug and is calculated as:

Exposure duration (days) = Last drug application date -First drug application date + 1 - (treatment interruption period)

The date from end of treatment phase is to be used for last drug application date.

Exposure as measured by amount tablets administered calculated as:

 $Actual\ exposure\ (tablets) = tablets\ dispensed-tablets\ returned$

Note that if any 'Amount Returned' field in the Drug Accountability CRF page is blank, then this formula will not be calculated.

If any of the first or last dates are missing or partially missing, then imputed dates will not be used, and study drug exposure is set to missing.

Total amounts of doses received will be calculated as number of days where at least one dose amount of >0 is administered. The first dose of the intervention period intended to be the SV3 dose and the intended last dose of the intervention period is SV7 dose.

Total time of exposure (patients-years) is calculated as:

Total time of exposure (patients – years) =
$$\frac{1}{365.25} \times \sum_{Patient} Exposure duration$$

4.7.1.2 Presentation

The duration of exposure and total amount of dose received will be summarised using descriptive statistics for each study intervention group and overall.

Duration of exposure and total dose will be presented by category, with categories being Days 1-28, 29-56, 57-84, 85-112, 113-140 and 141-172.

The total time of exposure will be displayed by intervention and overall.

In addition, a figure of exposure over time will be presented, with one line for each study intervention group, and percentage of participants still exposed on the y-axis and time from

first dose on the x-axis. At a given time t, the curve will show the percentage of participants with exposure time >t.

The total amount of dose will be summarised by intervention group and overall.

These outputs will be based on the SS.

Exposure details, such as duration of exposure, date of each treatment administration and dose per administration, will be listed for the Safety population.

4.7.2 Adverse Events

4.7.2.1 Definitions and Derivations

Adverse events (AEs) will be collected from the time of first dose of study intervention throughout the treatment and the follow-up periods (SV8). The only exception is related to the pre-dose orthostatic test at Visit SV3: if orthostatic hypotension is confirmed, it should be reported as an AE, and symptoms related to the measurement of orthostatic vital signs if present should also be reported as an AE.

Serious adverse events (SAEs) will be recorded from the time of signing of the ICF. AEs will be coded with MedDRA version 25.1 or higher and will be classified by SOC and PT. For any additional details on AE reporting please refer to the CSP.

AEs will be defined as treatment emergent adverse events (TEAEs) if they have an onset date on or after first dose date of study intervention until safety follow-up. AEs with a missing start date will be considered as TEAEs.

Any AE

Defined as an AE reported with an onset date within the defined period.

Any SAE

Defined as an AE reported as serious, irrespective of outcome.

SAEs with outcome death

Defined as an AE with reported outcome as 'Fatal', there may be more than one AE with outcome death for a patient. The onset date of the AE determines the analysis period, irrespective of date of death.

AEs leading to discontinuation of IP

Defined as an AE with action taken IP reported as drug permanently discontinued. The onset date of the AE determines the analysis period, irrespective of date of discontinuation of IP.

AEs possibly related to IP

Defined as an AE that is reported as "reasonable possibility AE caused by IP". If this evaluation is missing, it will be counted as an AE possibly related to IP.

AEs by maximum intensity

AEs will be classified by the reported maximum intensity, "Mild", "Moderate" and "Severe". If this maximum intensity evaluation is missing, it will be counted as "Severe".

Adverse events of special interest

The following AESIs will be particularly monitored in this study:

Skin reactions, including maculopapular rash:

- Skin reactions/rashes considered maculopapular (described as macules/papules under the morphology/appearance question).
- Skin reactions/rashes not considered maculopapular (not described as macules/papules under the morphology/appearance question).

Infections, including pneumonia will be defined by the SOC "Infections and infestations" or the pathogen specific High level group term (HLGT) "Fungal infectious disorders"

AEs will be assigned to a specific category based on investigator's judgement, using a checkbox on the AE CRF page.

4.7.2.2 Presentation

All AE summary tables and listings will be created by study intervention group for the SS, unless otherwise specified. TEAEs occurring during study intervention and follow-up period will be reported in summary tables including any related to the pre-dose orthostatic test at Visit SV3. All AEs will be listed in key subject information tables and listings.

Overview tables will contain number and percentage of participants and number of episodes in following categories:

Any AEs

Any AEs with outcome = death

Any SAEs (including events with outcome = death)

Any AE related to IP (as assessed by the Investigator)

Any AEs leading to discontinuation of IP

Any AEs leading to dose interruption

Any AEs leading to withdrawal from study

Any AESI

Any pneumonia or other serious infection

Any skin reaction

Any maculopapular rash

Any non-maculopapular rash

Any maculopapular rash leading to IP discontinuation, by maximum of CTCAE grade and overall

Any non-maculopapular rash leading to IP discontinuation, by maximum of CTCAE grade and overall

The number and percentage of participants with AE by SOC and PT will be summarised by study intervention group.

The number and percentage of participants with AEs occurring in >5% of participants in any study intervention group will be summarised by PT and study intervention group.

The number and percentage of participants with AEs by maximum reported intensity by SOC and PT will be summarised by study intervention group.

The number and percentage of participants with possibly-related AEs as assessed by investigator will be summarised by:

- SOC, PT and study intervention group
- SOC, PT, maximum grade of severity and study intervention group.

The number and percentage of participants with AEs with outcome of death by SOC and PT will be summarised by study intervention group. Key patient information for participants who experienced AEs with outcome of death will be produced for each study intervention group using following information:

Patient identifier

Sex

Age (years)

Race

Event term as reported by the investigator

PT

Time from first IP administration (days)

Time from last IP administration (days)

Time from last IP administration to death (days)

Time from first IP administration to death (days)

Reasonable possibility AE caused by IP

The number and percentage of participants with SAEs by SOC and PT will be summarised by study intervention group, the summary will be repeated to present number and percentage

of participants with related SAEs. Key patient information for participants who experienced SAEs will be produced using following information:

Study intervention group

Patient identifier

Sex

Age (years)

Race

Event term as reported by the investigator

PT

Time from first IP administration to onset of AE (days)

Time from last IP administration prior to onset of AE (days)

Time from start of IP administration to becoming serious

Outcome

Action taken with IP

Reasonable AE caused by IP

The number and percentage of participants with AEs leading to discontinuation of investigational product by SOC and PT will be summarised by study intervention group. Key patient information for participants who experienced AEs leading to discontinuation of IP will be produced using following information:

Study intervention group

Patient identifier

Sex

Age

Race

AE as reported by the investigator

PT term

Time from first IP administration to onset of AE (days)

Time from last IP administration prior to onset of AE (days)

Seriousness

Outcome

Reasonable possibility AE caused by IP

A list of PTs for AESIs will be produced.

Number and percentage of participants with AESIs will be summarised by category and PT for each study intervention group. Number and percentage of participants with serious AESIs will be summarised by category and PT for each study intervention group.

Number and percentage of participants with skin reactions will be summarised by category, PT and maximum CTCAE grade for each study intervention group. Number and percentage of participants with serious skin reactions will be summarised by category, PT and maximum CTCAE grade for each study intervention group. Additionally to the all AE listing, all skin reactions will be listed separately.

Number and percentage of participants with AESIs will be summarised by category, PT and maximum intensity for each study intervention group. Number and percentage of participants with serious AESIs will be summarised by category, PT and maximum intensity for each study intervention group.

Key patient information for participants who experienced AESI will be produced using following information:

Study intervention group

Patient identifier

Sex

Age

Race

AE Category

AE as reported by the investigator

PT term

Time from first IP administration to onset of AE (days)

Time from last IP administration prior to onset of AE (days)

Seriousness

Maximum Intensity (mild, moderate, severe)

Outcome

Reasonable possibility AE caused by IP

Key patient information for participants who experienced at least one positive sequence suggesting orthostatic hypotension (more details in Section 4.7.6) will be produced using following information:

Study intervention group

Patient identifier

Sex

Age

Race

AE as reported by the investigator

PT term

Time from first IP administration to onset of AE (days)

Time from last IP administration prior to onset of AE (days)

Seriousness

Maximum Intensity (mild, moderate, severe)

Outcome

Reasonable possibility AE caused by IP

Flag for event occurring within 3 hours after first dose of IP for baseline

BP values from VS

Key patient information for participants who experienced at least two positive sequence suggesting orthostatic hypotension (more details in Section 4.7.6) will be produced using same information as above.

Time to onset to maculopapular rash and grade 3 maculopapular rash will be summarised and time to onset to maculopapular rash will be displayed with box plots.

Narratives will be generated for all deaths, AEs leading to discontinuation of IP, AEs of Special interest and SAEs.

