8.3.2 Vital Signs

Vital signs (supine BP [average of 3 measurements], respiratory rate, pulse rate, and body temperature) will be performed in-clinic at timelines as specified in the SoA (Table 1).

Vital sign assessments are to be collected using equipment supplied by the investigator.

At Visits SV3 and SV5, the vital signs BP measurements can be used for the pre-dose supine measurements for the orthostatic test, if taken after being supine for at least 10 minutes and as long as the standing BP measurements are taken after these supine measurements at the time intervals described below for the orthostatic blood pressure measurement.

The measurements should be done before any blood sampling. The measurements should be preceded by at least 5 minutes of rest for the participant in a quiet setting without distractions.

Orthostatic Blood Pressure Measurements and Follow-up of Confirmed Orthostatic Hypotension

Orthostatic BP measurements will be obtained using a standard sphygmomanometer after scheduled supine measurements (1 and 3 minutes after the participant stands) and prior to any required blood draw:

- At SV3 (baseline; Day 1), orthostatic BP should be measured pre-dose and 1 to 2 hours post dose.
- At SV5 (Week 12), orthostatic BP should be measured pre-dose.

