To minimise chances of orthostatic hypotension related to volume depletion, participants should be well hydrated when they come to the clinic for study visits. Supine BP measures will be collected after participants have been lying down for at least 10 minutes. To ensure that a stable supine BP is obtained, at least 2 systolic and 2 diastolic BP measurements will be obtained. If the replicate measurements differ by no more than 10 mmHg and 5 mmHg, respectively, the supine BP will be considered stable. The mean value of each replicate (mean systolic and mean diastolic value) will represent the baseline BP for that visit. After stable BP is achieved, the participant will stand, and BP measurements will be taken at 1 and 3 minutes after the participant stands. If the BP measurements do not meet the criteria for orthostatic hypotension, no additional measurement is needed. If the BP measurement meets the criteria shown in Table 5, investigators will repeat the supine and standing measurements up to 2 additional times. The exception is for participants with orthostatic hypotension symptoms: in this situation, the orthostatic hypotension AE should be reported based on a single orthostatic test sequence.

When evaluating orthostatic vital signs, any symptoms of dizziness or light headedness should be recorded on the AE page in the eCRF. At Visit SV3, if orthostatic hypotension is confirmed pre-dose and post-dose, the orthostatic hypotension AE should be reported twice (pre-dose and post-dose). The same applies to symptoms related to the measurement of orthostatic vitals: if present pre-dose and post-dose, it should also be reported as an AE twice (pre-dose and post-dose).

Table 5 Orthostatic Blood Pressure Criteria and Management

Decrease in BP indicative of orthostatic hypotension	Actions
≥ 20 mmHg systolic or ≥ 10 mmHg diastolic	Repeat the BP measurements (supine and standing) up to 2 additional times, unless orthostatic hypotension is present in association with symptoms related to the measurement of orthostatic vitals: in such a case the test does not need to be repeated and the orthostatic hypotension AE and symptoms related to the measurement of orthostatic vitals AE should be reported based on a single sequence.

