8.4.1 Time Period and Frequency for Collecting AE and SAE Information

Adverse events will be collected from the time of first dose of study intervention throughout the treatment and the follow-up periods (SV8; Table 1). The only exception is related to the pre-dose orthostatic test at Visit SV3: if orthostatic hypotension is confirmed, it should be reported as an AE, and symptoms related to the measurement of orthostatic vital signs if present should also be reported as an AE.

Serious adverse events will be recorded from the time of signing of the ICF.

If the investigator becomes aware of an SAE with a suspected causal relationship to the IMP that occurs after the end of the clinical study in a treated participant, the investigator shall, without undue delay, report the SAE to AstraZeneca.

Participants should be reminded at each visit to contact the investigator immediately, if rash or skin reaction has developed.

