For each visit/timepoint, up to 2 additional orthostatic blood pressure sequences may be performed. For each sequence, the orthostatic hypotension is defined by a decrease (between supine value and values at 1 or 3 minutes after standing) of \geq 20 mmHg for SBP or \geq 10 mmHg for DBP. The orthostatic hypotension for the visit/timepoint is confirmed if 2 of 2 or 2 of 3 sequences have demonstrated hypotension or if symptoms are reported to have occurred at

any of the sequences. When orthostatic hypotension is confirmed, the investigator reports an "Orthostatic Hypotension" adverse event specifying the date and time.

Details about the orthostatic blood pressure assessment are described in Appendix A.

The following definitions will be applied:

- BP decrease: orthostatic hypotension derived from orthostatic BP data with at least 2 positive sequences (ie. 2 of 2 or 2 of 3).
- BP decrease reported as AE: "Orthostatic Hypotension" AE starting the same day on Day 1 Pre-dose, Day 1 Post-dose or within the same day of the 12 weeks measurement.

The three following timepoints will be considered:

- Day 1 pre-dose
- Day 1 post-dose
- Week 12

For BP decrease, the CRF visit/timepoint variables will be used. For BP decreased reported as AE, these timepoints should be derived from exposure dates and times, and "Orthostatic Hypotension" start dates and times.

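### Orthostatic findings made before the first dose are counted in the treatment-emergent AE tables, against the SAP's own definition of the pre-treatment period

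*SAP*

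**What the plan says.** **Collection.** At SV3, "orthostatic BP should be measured pre-dose and 1 to 2 hours post dose" (Protocol 8.3.2), so both tests fall on one calendar day. AE collection starts at first dose with a single exception, the SV3 pre-dose test: "if orthostatic hypotension is confirmed, it should be reported as an AE" (Protocol 8.4.1), and related symptoms are reported too. A participant positive at both tests has the AE reported twice (Protocol 8.3.2; SAP Appendix A).

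**AE tables.** SAP 4.7.2.1 calls AEs treatment-emergent "if they have an onset date on or after first dose date of study intervention until safety follow-up". SAP 4.7.2.2 adds that these "will be reported in summary tables including any related to the pre-dose orthostatic test at Visit SV3".

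**Periods.** SAP 3.3.2 ends the pre-treatment period before the date and timepoint of the first dose and starts the on-treatment period at that timepoint, with time of day stated explicitly.

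**Orthostatic table.** SAP 4.7.6.1 regards orthostatic hypotension at a timepoint as "confirmed if 2 of 2 or 2 of 3 sequences have demonstrated hypotension or if symptoms are reported to have occurred at" any sequence. For a symptomatic participant, Protocol Table 5 says "in such a case the test does not need to be repeated". The row summarised from measurements is narrower: "BP decrease: orthostatic hypotension derived from orthostatic BP data with at least 2 positive sequences". Beside it stands a second row, taken from the AE record. SAP 4.7.6.2 tabulates both by arm and timepoint.

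**The concern.** Protocol Table 2 lists blood pressure reduction, through alpha-1A adrenoceptor inhibition, as a potential risk, with orthostatic monitoring as part of the mitigation. An AE found before the first tablet says nothing about that risk. Counting it as treatment-emergent adds background to both arms, which can pull the between-arm ratio for orthostatic hypotension and its symptoms towards 1. It also raises episode counts in the overview table. And it leaves the SAP with two incompatible answers to when treatment begins.

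A secondary concern is that the measured 'BP decrease' row does not follow the confirmation rule given in the same section. The cases it can miss are the symptomatic ones.

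**Working it through.** The plan states no orthostatic rate or count, so there is no figure to reproduce. The check sets definitions side by side and then illustrates the size under stated assumptions.

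**1. Is a pre-dose SV3 event treatment-emergent?**
- By SAP 4.7.2.1: the onset date equals the first-dose date, so yes.
- By SAP 3.3.2: the onset precedes the timepoint of first dose, so it is pre-treatment.
- By SAP 4.7.2.2: it is placed in the summary tables regardless.

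The data to separate the two exist. SAP 3.3.1.4 says AE date and time are mandatory eCRF fields, and SAP 4.7.6.1 already uses exposure and AE times to assign orthostatic AEs to timepoints.

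**2. Possible dilution.** All rates below are assumptions. Let p be the post-dose risk in an arm and q the pre-dose risk, equal in both arms. If pre-dose and post-dose status are independent, the tabulated proportion is 1 − (1 − q)(1 − p).

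| p, active vs placebo | q | Tabulated | Ratio | Difference (points) |
|---|---|---|---|---|
| 10% vs 5% | 0 | 10.0% vs 5.0% | 2.00 | 5.0 |
| 10% vs 5% | 5% | 14.5% vs 9.75% | 1.49 | 4.75 |
| 10% vs 5% | 10% | 19.0% vs 14.5% | 1.31 | 4.5 |
| 10% vs 5% | 20% | 28.0% vs 24.0% | 1.17 | 4.0 |
| 8% vs 4% | 0 | 8.0% vs 4.0% | 2.00 | 4.0 |
| 8% vs 4% | 2% | 9.84% vs 5.92% | 1.66 | 3.92 |
| 8% vs 4% | 5% | 12.6% vs 8.8% | 1.43 | 3.8 |
| 8% vs 4% | 10% | 17.2% vs 13.6% | 1.26 | 3.6 |

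Example: 1 − 0.95 × 0.90 = 14.5%; 1 − 0.95 × 0.95 = 9.75%; 14.5 / 9.75 = 1.49.

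If instead every pre-dose case is also positive after dosing, the pre-dose event adds no new participant. With q = 5% the table still shows 10% vs 5%, ratio 2.0; only episodes rise. That pattern is possible only where q does not exceed p in either arm, so the two patterns illustrate the size rather than bound it.

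**3. Confirmation rule against the derived row.**

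| Sequences at one timepoint | Confirmed / AE | 'BP decrease' |
|---|---|---|
| 1 positive, symptoms, stopped | yes | no |
| positive then negative, symptoms | yes | no |
| 2 of 2, no symptoms | yes | yes |
| 2 of 3, no symptoms | yes | yes |
| 2 positive, symptoms | yes | yes |
| 1 of 3, no symptoms | no | no |

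The two rules disagree only for symptomatic participants with fewer than two positive sequences.

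**4. Timepoints.** SAP 4.7.6.1 names Day 1 pre-dose, Day 1 post-dose and Week 12. The Table 14.3.8.5 shell in SAP Appendix B names post first dose, only post first dose, and Week 12. The shell has no pre-dose column, and its middle column is not defined.

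**The case against.** The inclusion is disclosed, not hidden. The question of a drug effect on standing blood pressure is addressed mainly by Table 14.3.8.5, which splits findings by timepoint and whose 'only post first dose' column appears meant to isolate new cases. Safety is summarised descriptively, orthostatic hypotension is not an AE of special interest, and Protocol Table 2 reports no clinically relevant blood pressure change so far. All of this stands, and it limits the point to the general AE tables, which have no such split.

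Three stronger readings are tempting, and the documents do not support them.

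- *The SAP loses symptomatic cases.* A participant with symptoms and one sequence must be reported as an AE, so belongs in the paired AE row of the same table. If the sequence was positive, the participant also appears in the SAP 4.7.6.2 listing. Only the derived row omits them.
- *Symptomatic participants can never count as a 'BP decrease'.* A repeat is not required, but it is not forbidden; two positive sequences with symptoms do count.
- *A doubling of risk would be tabulated as 1.17.* That needs an assumed 20% pre-dose prevalence and independence. Postural drops may well recur in the same person, and full recurrence causes no dilution of percentages.

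Adding symptoms to a row defined from blood pressure data is also partly a matter of taste, because a clearer label would serve.

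**Conclusion.** The point holds for the AE tables. A date-only rule, together with an explicit instruction, places events that cannot be drug effects among treatment-emergent events, in conflict with SAP 3.3.2. The affected outputs are the overview, SOC/PT, intensity and >5% tables; where episodes are counted, a participant positive before and after dosing contributes two.

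The effect is descriptive and its size is unknown. It depends on pre-dose prevalence and on recurrence within participants, neither of which the documents give. In the illustrations the pull on the ratio runs from none under full recurrence to the tabulated values under independence. Under independence the risk difference falls by at most one percentage point.

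The mismatch between the derived row and the confirmation rule is real but secondary, as is the timepoint discrepancy. Severity is minor: the primary endpoint, alpha and power are unaffected.

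**What to change.** 1. In SAP 4.7.2.1 and 4.7.2.2, apply the time-of-day boundary of SAP 3.3.2 to Day 1 AEs. Class SV3 pre-dose orthostatic hypotension and related symptoms as pre-treatment, exclude them from the TEAE tables, and list them separately.
2. In SAP 4.7.6.1 and Table 14.3.8.5, either label the derived row as repeat-confirmed blood pressure decrease only, or add a row for one positive sequence with symptoms.
3. Use one set of timepoints in SAP 4.7.6.1 and the Table 14.3.8.5 shell, and define the 'only post first dose' column if it is kept.

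The cost is a few SAP sentences and a small programming change, with no new data for item 1. Relabelling under item 2 costs almost nothing. The extra row would require linking symptoms on the AE page to the test sequence, because the documents show no symptom field attached to a sequence.
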